## 7.0 STUDY AGENT ADMINISTRATION OR INTERVENTION AND TOXICITY MANAGEMENT PLAN

7.1 You will receive omadacycline administered in doses of 100 mg intravenously over 0.5 hour followed by a 1-week washout and receipt of 300 mg PO.

AGENT	DOSE	ROUTE	DAYS	ReRx	NOTES
Omadacycline	100 mg	I.V. over 0.5 hours	1	Once	
Omadacycline	300 mg	PO	1	Once	-Fast for at least 4hours and then take omadacycline tablet with water. -After oral dosing, no food or drink (except water) is to be consumed for 2 hours and no dairy products, antacids, or multivitamins for 4 hours.

## 7.2 Criteria for removal from the study

7.21 A patient may always be removed from study whenever he/she wishes.

7.22 A patient may be removed from the study if they experience an allergic reaction to the medication.

## 7.3 Ancillary treatments.

Patients may continue to take their medications for treatment of CF

## 8.0 ASSESSMENT OF EFFICACY AND SAFETY

### 8.1 Side effects/Toxicities to be monitored.

Possible side effects of Omadacycline are:

The most common adverse reactions (incidence  $\geq 2\%$ ) are nausea, vomiting, infusion site reactions, alanine aminotransferase increased, aspartate aminotransferase increased, gamma-glutamyl transferase increased, hypertension, headache, diarrhea, insomnia, and constipation.

In the pooled ABSSSI trials, serious adverse reactions occurred in 16/691 (2.3%) of patients treated with omadacycline and 13/689 (1.9%) of patients treated with comparator. Discontinuation of treatment due to adverse events occurred in 12 (1.7%) omadacycline treated patients, and 10 (1.5%) comparator treated patients. There was 1 death (0.1%) reported in omadacycline treated patients and 3 deaths (0.4%) reported in linezolid patients in ABSSSI trials.

The following selected adverse reactions were reported in omadacycline treated patients at a rate of less than 2% in these clinical trials:

- Gastrointestinal Disorders: abdominal pain, dyspepsia
- General Disorders and Administration Site Conditions: fatigue
- Immune System Disorders: hypersensitivity
- Infections and Infestations: oral candidiasis, vulvovaginal mycotic infection
- Investigations: creatinine phosphokinase increased, bilirubin increased, lipase increased, alkaline phosphatase increased
- Nervous System Disorders: dysgeusia, lethargy
- Respiratory, Thoracic, and Mediastinal disorders: oropharyngeal pain
- Skin and Subcutaneous Tissue Disorders: pruritus, erythema, hyperhidrosis, urticaria

8.11 Patients will be asked about the presence of nausea, vomiting, diarrhea, or headache.

8.12 CBC and CMP will be monitored at baseline

## 8.2 Adverse Event Reporting:

8.21 Any significant adverse events that occurs during the course of the study will be documented and reported.

8.22 Reports will be submitted to: IRB, FDA (MedWatch)

8.3 Data Monitoring Committee (if applicable)  
Not applicable

## 9.0 CLINICAL AND LABORATORY EVALUATIONS AND STUDY CALENDAR

See Appendix III: Study Calendar

## 10.0 CRITERIA FOR EVALUATION AND ENDPOINT DEFINITIONS

### 10.1 Criteria for Evaluation

The outcome status (in terms of toxicity, response, reason off study) of all eligible patients will be reported. All eligible patients who begin treatment will be included in the analysis.

### 10.2 Endpoint Definitions

PK parameters of omadacycline including the area under the curve, maximum concentration and time to maximum concentration in patients with CF.

## 11.0 SPECIAL INSTRUCTIONS:

Blood samples will be obtained predose, 0.25, 0.5, 1, 2, 3, 4, 8, 12, 24, 48, and 72 hours after the end of the IV infusion and oral dose.

Blood samples will be processed, and aliquots of plasma will be stored at -80°C until assayed for omadacycline.

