
The pharmacokinetics of a number of medications have shown to be altered in patients with CF [11,12]. In general, patients with CF demonstrate an increased volume of distribution when expressed in L/Kg of body weight, and increased total body clearance. In addition, the oral bioavailability of lipophilic medications is reduced due to pancreatic insufficiency. To our knowledge no study has evaluated the pharmacokinetics of omadacycline in patients with CF. The proposed study is designed to characterize the pharmacokinetics of intravenous and oral omadacycline in patients with CF and determine the optimal dosing regimen in preparation for future efficacy and safety studies in CF patients with MABSC lung infections.

The pharmacokinetics of omadacycline in healthy volunteers, special populations, and patients with complicated skin and skin structure infections has been well described [7-9]. The oral absorption is relatively rapid and the bioavailability is good. Of note is the reduced bioavailability observed with high-fat meals or in conjunction with dairy products; based on these observations omadacycline is recommended to be given under fasting conditions with no food or dairy/antacids/multivitamins for 2 and 4 hours after administration respectively [10]. Elimination of omadacycline occurs predominately through fecal excretion [10]. No dosage adjustment is necessary for renal or hepatic disease [10].

Of particular importance to the proposed study is the excellent pulmonary penetration of omadacycline noted in healthy volunteers [9]. Bronchoalveolar lavage studies performed at

steady-state following omadacycline 100mg IV daily revealed epithelial lining fluid and alveolar macrophage exposures 2-fold and 30-fold higher respectively, than free drug exposures in plasma. These exposures also exceeded that of tigecycline indicating greater pulmonary penetration with omadacycline.

Our study hypothesis is that omadacycline will exhibit good oral bioavailability in patients with CF.

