## 13.0 DATA/STATISTICAL CONSIDERATIONS

### 13.1 Pharmacokinetic analysis

Pharmacokinetics will be performed using standard noncompartmental methods.

The maximum concentration and time to maximum concentration will be from the

observed data. The area under the curve will be calculated using the trapezoidal rule. Absolute bioavailability will be determined by a ratio of the  $AUC_{PO}/AUC_{IV}$ .

In addition, population pharmacokinetic analysis will be performed using the maximum likelihood estimation via the EM algorithm with sampling (MLEM) as implemented in ADAPT 5 (Biomedical Simulations Resource, University of Southern California). Multiple candidate models will be evaluated to identify the model that best describes the observed plasma concentration data.

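### No IV sample is scheduled at the end of the 0.5 h infusion, so observed IV Cmax falls below the true peak and IV Tmax mostly reports the first draw

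*Combined protocol and SAP*

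**What the plan says.** Section 7.1 of the combined protocol and SAP describes "omadacycline administered in doses of 100 mg intravenously over 0.5 hour followed by a 1-week washout", after which the oral dose is given.

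Section 11.0 lists blood samples at "predose, 0.25, 0.5, 1, 2, 3, 4, 8, 12, 24, 48, and 72 hours after the end of the IV infusion"; the same list serves the oral dose. It includes no 0 h post-infusion sample and none during the infusion.

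Section 10.2 defines the endpoints as "PK parameters of omadacycline including the area under the curve, maximum concentration and time to maximum concentration in patients with CF".

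Section 13.1 sets out how each is obtained:
- For Cmax and Tmax: "The maximum concentration and time to maximum concentration will be from the" data as observed.
- For AUC: "The area under the curve will be calculated using the trapezoidal rule", without saying which version of the rule.
- For F: "Absolute bioavailability will be determined by a ratio of the" oral to IV AUC.
- A second analysis is also planned: "population pharmacokinetic analysis will be performed using the maximum likelihood estimation via the EM algorithm with sampling (MLEM"), run in ADAPT 5. The text does not say that the model will supply Cmax or AUC.

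**The concern.** Under linear disposition, the concentration during a constant-rate infusion rises until the infusion stops and falls from then on. The first post-dose IV sample comes 0.25 h into that fall. An IV Cmax read from the samples is therefore a point on the distribution slope, and IV Tmax tends to return the first sampling time whatever the drug does. A larger sample would not remove this, and the missing concentration cannot be measured later.

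Two of the three named endpoints are affected in the IV period. There is also a risk of misreading. Section 1.0 says that "patients with CF demonstrate an increased volume of distribution when expressed in L/Kg of body weight", and it describes omadacycline pharmacokinetics in healthy volunteers as already well characterised. A reader who compares IV Cmax with healthy-volunteer values could take a shortfall caused by the schedule for a CF effect.

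The IV AUC is touched as well. The first trapezoid joins the predose zero directly to the 0.75 h value and cuts off the peak. IV AUC is the denominator of absolute bioavailability, F.

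**Working it through.** The plan states no figure to reproduce. The check compares what the schedule would record with the exact curve.

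**Inputs from the documents.** Infusion time T = 0.5 h (section 7.1). Samples at predose and at 0.5 h plus 0.25, 0.5, 1, 2, 3, 4, 8, 12, 24, 48 and 72 h, counted from the start of infusion (section 11.0).

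**Assumed inputs.** The documents give no disposition parameters, so two ranges were used.
- Narrower range: distribution half-life 0.15–1.0 h, 60–85% of the initial concentration in the distribution phase, terminal half-life 12–24 h.
- Wider range: distribution half-life 0.1–2 h, terminal half-life 4–24 h, ratio of fast to slow coefficients 0–8 (84 scenarios, where 0 means one compartment).

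**Formulas.** With coefficients Aᵢ and rates λᵢ = ln 2 / half-life:
- End of infusion: C(T) = Σ Aᵢ/(λᵢT) × (1 − e^(−λᵢT)).
- First sample: each term of C(T) is multiplied by e^(−0.25λᵢ).

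**One scenario in full.** Coefficient ratio 4:1, distribution half-life 0.5 h, terminal half-life 16 h, so λ₁ = 1.386 and λ₂ = 0.0433 per hour.
1. Peak: 4/(1.386 × 0.5) × (1 − 0.5) = 2.885, plus 1/(0.0433 × 0.5) × (1 − 0.9786) = 0.989. Sum 3.875.
2. First sample: 2.885 × 0.7071 = 2.040, plus 0.989 × 0.9892 = 0.979. Sum 3.019.
3. Observed/true Cmax = 3.019/3.875 = 0.779, a shortfall of 22.1%.
4. First AUC segment by trapezoid: 0.75 × 3.019/2 = 1.132. The exact area over 0–0.75 h is 1.908, so the segment is 40.7% too low.
5. That deficit, 1.908 − 1.132 = 0.776, is 3.1% of the exact AUC(0–72.5 h) of 24.96.
6. Total AUC: linear-up/log-down gives 24.26 (−2.8%); linear gives 25.07 (+0.4%).
7. With a sample at the end of infusion: linear-up/log-down gives 24.96 (0.0%); linear gives 25.76 (+3.2%).

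**Across the assumed ranges** (narrower: AUC extrapolated to infinity; wider: AUC to 72.5 h):

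| Quantity | Narrower range | Wider range |
|---|---|---|
| Observed/true IV Cmax | 0.522–0.908 (shortfall 9–48%) | shortfall 0.7–59% |
| First AUC segment | 40–69% of true | 26–69% too low |
| Total AUC, linear-up/log-down, as scheduled | 94.9–99.3% of true | −15.7% to −0.4% |
| Total AUC, linear, as scheduled | 99.0–102.9% | −10.6% to +5.3%, positive in 59 of 84 |
| Linear-up/log-down, sample added | 99.2–100.6% | −3.3% to +1.2% |
| Linear, sample added | 101.3–104.6% | +1.3% to +6.7% |

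Under the linear rule, the wide late intervals (12–24, 24–48 and 48–72 h) overstate a convex decline. This can offset or exceed the early loss. Apparent accuracy under that rule is two errors cancelling.

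**Effect on F.** If AUC_IV is a fraction k of true and AUC_PO is held exact, F is multiplied by 1/k. On the narrower range this is 1/0.993 = 1.007 to 1/0.949 = 1.054 under linear-up/log-down, and 1/1.029 = 0.972 to 1/0.990 = 1.010 under the linear rule. AUC_PO carries trapezoidal error of its own, so the net effect can be smaller; with simulated oral profiles F rose by about 1–3% when its IV denominator was too low.

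**Assay error.** Without noise, IV Tmax is always the first sample, 0.75 h from the start. With 5–15% assay CV, it falls on the first sample in 49–100% of patients in the two-compartment scenarios tested and 28–44% in a flat one-compartment scenario.

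**Moving a draw instead of adding one.** Dropping the 3 h sample and taking one at the end of infusion gives a linear-up/log-down AUC of 99.2–100.9% of true on the narrower range.

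**The case against.** Several parts of the opposing case stand.

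- **IV AUC understated and F inflated.** A reader might infer both from the clipped peak. The documents do not support it, because section 13.1 names no trapezoidal rule and under the linear rule total IV AUC is more often overstated. Adding the sample while keeping the linear rule would take AUC further from true throughout the narrower range, though not everywhere on the wider one: with ratio 8 and half-lives of 0.25 h and 4 h, the error goes from −10.6% to +3.4%.
- **Every patient misses the peak and Tmax is fixed.** This is exact only without assay or timing error. With ratio 1, half-lives of 0.5 h and 16 h and 10% assay CV, the probability that all 12 observed values lie below the true peak is 0.33. In the flat one-compartment scenario, noise lifts most observed maxima above it.
- **The infusion interval will be dropped from the time axis.** IV times are counted from the end of infusion, so a reader might fear this. Section 13.1 specifies standard noncompartmental methods, and nothing says that nominal post-infusion times will be the axis. It is a reason for a clarifying sentence, not a finding.
- **Bias toward the study's own expectation.** The stated hypothesis concerns oral bioavailability. Volume of distribution is not among the parameters named in section 10.2, and no comparator or formal test is planned. Only the risk of misreading remains.
- **Population modelling.** The planned model can represent the infusion and predict the end-of-infusion concentration. This lessens the gap but does not close it: Cmax is committed to observed data, and the model would be predicting a peak at a time with no sample.
- **Little value in IV Tmax.** True in any design; with the added sample it would usually be 0.5 h. The case for the change rests mainly on Cmax.
- **Appendix III.** The study calendar cited in section 9.0 is not in the text available and may list an end-of-infusion draw. Section 11.0 would then need reconciling with it.

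**Conclusion.** The point holds for Cmax and Tmax. Section 11.0 schedules no sample where a 0.5 h infusion peaks, and section 13.1 reads both endpoints from the samples. Under linear disposition, the concentration at the first draw lies below the peak in every scenario examined, and IV Tmax is largely a product of the schedule.

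The direction of the Cmax shortfall rests on linear disposition and constant-rate input. Its size rests on assumed parameters, and the documents cannot narrow it: it could be negligible if early distribution is minor and large if distribution is fast.

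For AUC, only the deficit in the segment from predose to the first sample is established. The sign of the total IV AUC error, and of its effect on F, is open until the trapezoidal rule is named. In a descriptive 12-patient study those effects are secondary. The change is worth making because a named endpoint is distorted by design and the remedy is nearly free.

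**What to change.** 1. **Section 11.0:** schedule an IV-period sample at the end of infusion (0 h post-infusion), either added or obtained by moving one mid-phase IV draw such as the 3 h sample.
2. **Section 13.1:** specify linear-up/log-down trapezoids. The rule and the sample belong together, since on the narrower assumed range the sample improves AUC under this rule and worsens it under the plain linear rule.
3. **Section 13.1:** state that IV times run from the start of infusion, using recorded start and stop times.
4. **Appendix III:** if it already lists an end-of-infusion draw, bring section 11.0 into line with it.

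The cost is at most one extra small blood draw per patient, 12 in all, or slightly sparser sampling between 2 and 4 h if a draw is moved, plus two or three sentences of text.

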## 12.0 DATA COLLECTION AND MONITORING

Data will be collected on case report forms, which will be retained for the duration of the study. Data will include subject demographics, clinical characteristics, laboratory data, and results of pharmacokinetic analyses. Data will be coded and stored on a password protected electronic database.

## 13.0 DATA/STATISTICAL CONSIDERATIONS

### 13.1 Pharmacokinetic analysis

Pharmacokinetics will be performed using standard noncompartmental methods.

The maximum concentration and time to maximum concentration will be from the

observed data. The area under the curve will be calculated using the trapezoidal rule. Absolute bioavailability will be determined by a ratio of the  $AUC_{PO}/AUC_{IV}$ .

In addition, population pharmacokinetic analysis will be performed using the maximum likelihood estimation via the EM algorithm with sampling (MLEM) as implemented in ADAPT 5 (Biomedical Simulations Resource, University of Southern California). Multiple candidate models will be evaluated to identify the model that best describes the observed plasma concentration data.

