## 3.0 STUDY DESIGN

This study will be conducted using a prospective single dose, single-arm design to characterize the pharmacokinetics of omadacycline intravenous/oral (IV/PO) in CF. A total of 12 adult patients with CF will participate in the study and will receive a single dose of omadacycline 100mg IV followed by a 1-week washout and receipt of 300 mg PO.

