## 4.0 DRUG/DEVICE INFORMATION

4.1 Omadacycline (Nuzyra) is a tetracycline class antibacterial indicated for the treatment of adult patients with the following infections caused by susceptible microorganisms:

Community-acquired bacterial pneumonia (CABP)

Acute bacterial skin and skin structure infections (ABSSSI)

The recommended dosage of omadacycline is 300 mg administered once daily orally (tablet) or as an intravenous infusion (IV) of 100 mg over 0.5 hour for 7-14 days.

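### Section 13.1 defines absolute bioavailability as AUC_PO/AUC_IV with no dose term, although the oral and IV doses differ three-fold; applied as written, it gives three times the dose-normalised ratio.

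*Combined protocol and SAP*

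**What the plan says.** All references are to the combined protocol and SAP.

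- **Formula.** Section 13.1 opens with a general statement: "Pharmacokinetics will be performed using standard noncompartmental methods". It then says "The area under the curve will be calculated using the trapezoidal rule", without giving the interval over which the AUC is taken. The definition of F follows: "Absolute bioavailability will be determined by a ratio of the" AUC_PO/AUC_IV. No dose appears in it.
- **Doses.** Section 3.0 gives each patient a "single dose of omadacycline 100mg IV followed by a 1-week washout and receipt of 300 mg PO". Section 7.1 agrees: "doses of 100 mg intravenously over 0.5 hour followed by a 1-week washout and receipt of 300 mg PO". Section 4.1 lists the same two amounts as the recommended dosage: "300 mg administered once daily orally (tablet) or as an intravenous infusion (IV) of 100 mg".
- **Role of F.** The hypothesis at the end of section 1.0 is that oral bioavailability in CF will be good; no threshold is set. Section 2.0 makes plasma concentrations the primary objective. Section 10.2 lists AUC, maximum concentration and time to maximum, and does not name F. Section 13.2 describes the endpoints as descriptive.
- **Second analysis.** Section 13.1 adds a population pharmacokinetic model fitted in ADAPT 5. It does not say that F will be estimated there.

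No section mentions dose normalisation, dose-adjusted AUC or AUC per mg.

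**The concern.** Absolute bioavailability compares oral with IV exposure per unit of dose. When the doses differ, the raw AUC ratio combines two things: the fraction absorbed and the ratio of the doses. With 300 mg oral against 100 mg IV, the quantity defined in section 13.1 is the relative exposure of these two regimens. That is a legitimate quantity, but it is not the one the sentence names.

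At stake is the single number a reader would use to judge the hypothesis. Section 1.0 raises reduced oral bioavailability of lipophilic drugs in CF as a reason for concern, and says the study should help to determine a dosing regimen for later trials. An F inflated three-fold would mislead on both counts. Because the analysis is descriptive and sets no threshold, no formal test would bring the error to light.

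**Working it through.** The plan states no numerical value of F, so there is no figure to reproduce. The check is algebraic, followed by a sensitivity calculation.

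**Inputs from the documents**

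- Dose_IV = 100 mg and Dose_PO = 300 mg (sections 3.0 and 7.1, which agree).
- Formula as written: R = AUC_PO/AUC_IV (section 13.1).
- Blood samples before dosing and at 0.25, 0.5, 1, 2, 3, 4, 8, 12, 24, 48 and 72 hours, counted from the end of the infusion or from the oral dose (section 11.0). None is scheduled at the end of the infusion itself.

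**Step 1: the dose-normalised ratio**

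F = (AUC_PO/Dose_PO)/(AUC_IV/Dose_IV) = (AUC_PO/AUC_IV) × (100/300) = R/3.

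**Step 2: ratio of the two formulas**

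R/F = Dose_PO/Dose_IV = 300/100 = 3. The AUCs cancel, so this is exact for any pair of AUCs in any patient.

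**Step 3: what would be reported**

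| Dose-normalised F | Formula as written (3 × F) |
|---|---|
| 0.05 | 0.15 |
| 0.20 | 0.60 |
| 1/3 | 1.00 |
| 0.35 | 1.05 |
| 0.50 | 1.50 |
| 1.00 | 3.00 |

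The break point is 3 × F = 1, that is F = 1/3. Above it, the reported value exceeds 100%.

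**Step 4: comparison with true F**

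Steps 1 to 3 compare two formulas applied to the same AUCs. True F is a different comparator, because a trapezoidal AUC from finite sampling is itself approximate. To see by how much, a linear disposition model (one- or two-compartment) was sampled at the section 11.0 times, with a linear trapezoid up to the 72-hour sample. The pharmacokinetic values are assumptions, not figures from the documents: terminal half-life 8 to 24 hours, absorption rate constant 0.3 to 2.0 per hour, distribution phase from absent to marked, and F = 0.35. The written ratio divided by true F ran from about 2.95 to 3.29. Against true F, then, the factor is approximately 3, and it also depends on dose-linear kinetics, the AUC interval and the missing end-of-infusion sample.

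**The case against.** The strongest reply is that the sentence is shorthand. Section 13.1 promises standard noncompartmental methods, and by convention these divide each AUC by its dose; the formula may simply name the two AUCs to be compared. This stands to the extent that the documents show an incomplete formula, not an intention to leave dose out. A reader might infer that the published F will certainly be wrong; that holds only if the formula is applied literally. But the general statement does not repair the specific formula that follows it. An analyst who follows the plan gets the wrong quantity, and one who normalises departs from the written definition.

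A second reply is that the population model takes the actual doses as inputs. An F estimated there would not carry this error, but the plan does not say that F will be estimated there.

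Third, F is neither the primary objective nor a listed endpoint, and both AUCs and both doses will be on record, so the number can be corrected later from the same data. This is true, and it limits the damage. It does not make the stated definition right.

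A reader might also infer that the formula would support the hypothesis whatever the true absorption. The documents do not bear that out. With no threshold for good and no test, there is no decision rule to bias. A very low F would still look low (0.05 becomes 0.15), and an F above one third would give a value over 100% that should be noticed. The risk of an undetected error lies at or below about one third.

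**Conclusion.** The definition is wrong as written and should be corrected before the analysis. Applied literally, it gives exactly 3 times the dose-normalised ratio of the same AUCs. That result needs only the two doses in sections 3.0 and 7.1.

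It would be tempting to say that the reported F is exactly three times the true F. The documents do not support this: the exact factor is between two formulas, and the factor against true F is approximate under the assumptions in the working. Nor do they support the inference that the two recommended doses in section 4.1 give equal exposure, so that F is about one third and the formula would return about 100%; no section says that the doses are exposure-matched.

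The AUC, maximum concentration and time to maximum for each route are unaffected, as are the doses, sampling times and sample size. What is misstated is the one derived quantity that speaks directly to the study hypothesis.

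**What to change.** Replace the bioavailability sentence in section 13.1 with:

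> Absolute bioavailability F = (AUC_PO × Dose_IV)/(AUC_IV × Dose_PO) = (AUC_PO × 100)/(AUC_IV × 300), calculated within each patient using the same stated AUC interval for both routes.

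State that interval in the same section (for example, to 72 hours or extrapolated to infinity), since the trapezoidal sentence leaves it open. If the unadjusted ratio is also wanted, report it separately as the relative exposure of 300 mg oral to 100 mg IV, and do not call it bioavailability. If F is also to be estimated in the population model, say so.

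The cost is a sentence or two of text. Neither dose changes, and no extra samples or patients are needed. For the same AUCs, the stated F becomes one third of what the current formula would give.
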